4.2. Extent of Study Drug Exposure and Adherence

Extent of exposure to study drug will be examined by assessing the total duration of exposure to study drug.

Summaries of extent of study drug exposure and adherence will be provided by:

- Blinded Treatment phase
- OL Treatment phase

4.2.1. Duration of Exposure to Study Drug

Total duration of exposure to study drug will be defined as last dosing date minus first dosing date plus 1, regardless of any temporary interruptions in study drug administration, and will be expressed in weeks using up to 1 decimal place (e.g., 4.5 weeks). If the last study drug dosing date is missing, the latest date among the study drug end date, clinical visit date, laboratory sample collection date, and vital signs assessment date that occurred during the on-treatment period will be used for subjects included in the final analyses or the last available date in the database snapshot for subjects who were still on treatment at the time of an interim analysis.

The total duration of exposure to study drug will be summarized using descriptive statistics and using the number (i.e., cumulative counts) and percentage of subjects exposed through the following time periods:

- Blinded Treatment phase: 1 day, 4 weeks, 6 weeks, 10 weeks, 14 weeks, 18 weeks, 22 weeks, 26 weeks, 30 weeks, 34 weeks, 38 weeks, 42 weeks, 46 weeks and 50 weeks
- OL Treatment phase: 1 day, 4 weeks, 6 weeks, 10 weeks, 14 weeks, 18 weeks, 22 weeks, 26 weeks, 30 weeks, 34 weeks, 38 weeks, 42 weeks, 46 weeks and 50 weeks

Summaries will be provided by treatment group for the Safety Analysis Set. No formal statistical testing is planned.

A by-subject listing of study drug administration will be provided separately by subject ID number (in ascending order) and visit (in chronological order).

4.3. Protocol Deviations

Subjects who did not meet the eligibility criteria for study entry but enrolled in the study, will be summarized regardless of whether they were exempted by the sponsor or not. A by-subject listing will be provided for those subjects who did not meet at least 1 eligibility (inclusion or exclusion) criterion. The listing will present the eligibility criterion (or criteria if more than 1 deviation) that subjects did not meet and related comments, if collected.

Protocol deviations occurring after subjects entered the study are documented during routine monitoring. A by-subject listing will be provided for those subjects with important protocol deviation.

This study was ongoing during the coronavirus disease 2019 (COVID-19) pandemic. A by-subject listing will be provided for subjects with important protocol deviations related to COVID-19, if applicable. A separate listing will be provided for subjects with non-important protocol deviation related to COVID-19.

5. BASELINE CHARACTERISTICS

5.1. Demographics and Baseline Characteristics

Subject demographic variables (i.e., age, sex, race, and ethnicity) and baseline characteristics (body weight [in kg], height [in cm], and body mass index [BMI; in kg/m²]) will be summarized by treatment group and overall using descriptive statistics for continuous variables and using number and percentage of subjects for categorical variables. The summary of demographic data will be provided for the Safety Analysis Set.

A by-subject demographic listing, including the informed consent date, will be provided by subject ID number in ascending order.

5.2. Other Baseline Characteristics

The following baseline disease characteristics will be summarized by treatment group and overall using descriptive statistics for continuous variables and using number and percentage of subjects for categorical variables:

- Duration of UC (in years) from date of diagnosis to first dosing date
- MCS
- Partial MCS (pMCS)
- Endoscopic subscore of 3 (yes, no)

The summary of these baseline characteristics will be provided for the Safety Analysis Set. No formal statistical testing is planned.

A by-subject listing of baseline disease characteristics will be provided by subject ID number in ascending order. The following baseline disease characteristics will also be included in the listing:

- Extent of UC from medical history
- UC treatment history
 - Prior use of biologic agents (yes, no)
 - Number of TNF α antagonist used (1, 2, \geq 3)
 - Prior use of vedolizumab (yes, no)
 - Prior use of ustekinumab (yes, no)

- UC concomitant medication
 - Systemically absorbed corticosteroids (yes, no)

5.3. Medical History

The extent of UC will be included in the by-subject listing of baseline disease characteristics. Other medical history data will not be summarized or listed.

6. EFFICACY ANALYSES

6.1. General Considerations

The efficacy analysis will be conducted on the FAS, defined in Section 3.1.2, unless otherwise specified.

The definitions for the key efficacy endpoints (i.e. primary and key secondary efficacy endpoints) are listed in Table 6-1. All of the key efficacy endpoints are dichotomous.

Table 6-1. Definitions for Primary and Key Secondary Efficacy Endpoints

Type	Event Endpoint	Definition
Primary	Clinical Remission per Modified MCS at Week 10	Stool Frequency subscore ≤ 1 and not greater than baseline, Rectal Bleeding subscore of 0, and Endoscopic subscore ≤ 1 at Week 10
Secondary	Endoscopic Response at Week 10	Endoscopic subscore ≤ 1 at Week 10
Secondary	MCS Response at Week 10	A decrease from baseline of ≥ 3 points and at least 30% in MCS, in addition to a ≥ 1 point decrease from baseline in the Rectal Bleeding subscore or a Rectal Bleeding subscore ≤ 1 at Week 10
Secondary	MCS Remission at Week 10	MCS score of ≤ 2 and no individual subscore > 1 at Week 10
Secondary	Histologic Remission at Week 10	Geboes Scale with all of the following must be met at Week 10: Grade 0 of ≤ 0.3 , Grade 1 of ≤ 1.1 , Grade 2a of $\leq 2A.3$, Grade 2b of 2B.0, Grade 3 of 3.0, Grade 4 of 4.0, and Grade 5 of 5.0 {Geboes 2000}

For each of the key efficacy endpoints defined above, responders are subjects who achieved the endpoint based on assessment. Subjects who do not have sufficient measurements to determine the endpoint will be considered non-responders (i.e., non-responder imputation [NRI]).

MCS Response at Week 10 will be used to determine whether a subject is eligible to continue Blinded Treatment phase or enter OL Treatment phase. Subjects with insufficient data to assess MCS Response will discontinue study drug and are not eligible for the OL Treatment phase, even if they are considered as non-responder by NRI.

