5.4.1. Allowed Concomitant Medications for UC

The allowed concomitant medication(s) for UC should be maintained at a stable dose for the duration of the study. Subjects on corticosteroids for the treatment of UC at the time of randomization should initiate a steroid taper after the Week 10 Visit (Section 5.4.1.1).

The allowed medications for UC are as follows:

- Oral mesalamine compounds (5-ASA) provided the dose prescribed has been stable for at least 4 weeks prior to randomization.
- Thiopurines (eg, azathioprine, 6-MP) and methotrexate provided the dosing duration must be for at least 8 weeks prior to randomization and the dose must have been stable for at least 4 weeks prior to randomization
- Systemically absorbed corticosteroids prescribed at a stable dose equivalent to ≤ 30 mg/day prednisone or budesonide prescribed at a stable dose of ≤ 9 mg/day. The doses prescribed must have been stable for 2 weeks prior to the screening endoscopy.

Due to the potential for drug-drug interactions, sulfasalazine is prohibited from 2 weeks prior to the screening endoscopy and throughout treatment with study drug.

Changes to allowed concomitant medications for UC may confound the efficacy and safety assessments of GS-4875. Therefore, subjects who start or increase the dose (compared with the dose at Day 1) of the above allowed concomitant medications, during either the Blinded Treatment phase or the OL Treatment phase, must discontinue study drug and study participation.

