6.5.2. Week 10 – Blinded Treatment & Open-Label Treatment Phases

The Blinded Treatment phase assessments to be completed at this visit are outlined in the Study Procedures Table in [Appendix 2](#) and the OL Treatment phase assessments to be completed at these visits are outlined in the Study Procedures Table in [Appendix 3](#) with additional information on assessments provided in Sections 6.8 to 6.12.

At this visit, all subjects will have an efficacy assessment that includes a Colonoscopy/Flexible Sigmoidoscopy with collection of biopsies. Subject diary data entry should be reviewed prior to performing the Week 10 endoscopy to ensure subjects have sufficient data entry to calculate Week 10 MCS subscores. Following the visit, the Endoscopic Findings will be provided to the sites after central read. The value provided by the central reader and the PGA is to be recorded by the investigator (or designee) for central calculation of MCS and subject MCS Response determination.

Until response can be assessed based on Week 10 results, subjects will continue on their current assigned study drug regimen. In the Blinded Treatment Phase, subjects who achieve MCS Response (Section 2) based on results from Week 10 will continue in the Blinded Treatment phase. Subjects who do not achieve MCS Response (Section 2) at Week 10 will have the option to enter the OL Treatment phase. Subjects with incomplete data to assess MCS Response will discontinue study drug and are not eligible for the OL Treatment phase.

In the OL Treatment phase, subjects who achieve MCS Response (Section 2) at Week 10 will continue in the OL Treatment phase. All other subjects will discontinue the OL Treatment phase. Subjects with incomplete data to assess MCS Response will discontinue study drug.

6.5.3. Weeks 14, 18, 22, 26, 30, 34, 38, 42, and 46 - Blinded Treatment & Open-Label Treatment Phases

The Blinded Treatment phase assessments to be completed at these visits are outlined in the Study Procedures Table in [Appendix 2](#) and the OL Treatment phase assessments to be completed at these visits are outlined in the Study Procedures Table in [Appendix 3](#) with additional information on assessments provided in Sections 6.8 to 6.12.

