6.9.2. Review of Concomitant Medications

Review all medications taken up to 30 days prior to the screening visit through the end of study (30 days after the last dose of study drug). At each study visit, record all medications taken by the subject since the last visit or during the visit (as applicable). All concomitant medications (prescription, peri-procedural medications, over-the-counter medications, including vaccines, vitamins, herbal, dietary supplements, and minerals) must be recorded.

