8.5. Efficacy Analysis

8.5.1. Primary Analysis

The primary analysis will compare each GS-4875 dose group to placebo on the proportion of subjects achieving Clinical Remission per Modified MCS at Week 10. The Cochran-Mantel-Haenszel (CMH) approach adjusting for stratification factors will be used for hypothesis testing of the primary endpoint. For evaluation of clinical remission per modified MCS at Week 10, MCS score at screening will be used as baseline value.

Subjects who do not have sufficient measurements to determine efficacy endpoints will be considered failures (ie, non-responder imputation [NRI]).

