1.3. Sample Size and Power

A total of 180 subjects, i.e. 60 subjects in the placebo group and 60 subjects in each GS-4875 dose group (n = 120 total for GS-4875), will provide approximately 75% power when comparing each GS-4875 dose group to placebo at a 1-sided 0.025 significance level to detect a treatment difference in clinical remission rate per modified MCS of 17.5% (22.5% on GS-4875 and 5% on placebo) based on Fisher's exact test.

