7.4. Prior and Concomitant Medications

Medications collected at screening and during the study will be coded using the current version of the World Health Organization (WHO) Drug dictionary.

UC-specific prior and concomitant medications at baseline will be included in the listing of other baseline characteristics as described in Section 5.2. No other prior and concomitant medications will be summarized or listed.

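### Non-response is triggered only by missing measurements, so a subject whose added UC therapy is not caught before the Week 10 endoscopy can be listed as a remitter or responder

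*SAP*

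**What the plan says.** **Analysis rule.** SAP 6.1 takes responders to be those who meet the endpoint on assessment and adds that "Subjects who do not have sufficient measurements to determine the endpoint will be considered non-responders". Protocol 8.5.1 says that "Subjects who do not have sufficient measurements to determine efficacy endpoints will be considered failures", and 8.5.2 repeats this for the binary secondary endpoints. SAP Table 6-1, SAP 3.6.1 (missing data), SAP 3.8.2 (visit windows) and SAP Appendix 4 (score calculation) attach no condition about added UC therapy or about still being on study drug.

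**Conduct rules.**
- Protocol 5.4.1 addresses "subjects who start or increase the dose (compared with the dose at Day 1) of the above allowed concomitant medications". These subjects must leave both study drug and the study.
- Protocol 6.13.3 covers the same kind of change but mentions study drug only.
- Protocol 5.4.2 requires a subject who starts a Table 5-2 agent to stop study drug, and bars entry to the open-label phase.

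**Detection.** Protocol 6.9.2 instructs: "At each study visit, record all medications taken by the subject since the last visit or during the visit". Before the Week 10 procedure, Protocol 6.5.2 asks for one specific check: "Subject diary data entry should be reviewed prior to performing the Week 10 endoscopy".

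**Reporting.** SAP 5.2 lists UC concomitant medication as systemic corticosteroids, yes or no. SAP 7.4 adds: "No other prior and concomitant medications will be summarized or listed".

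**The concern.** Corticosteroids, rectal preparations and antidiarrhoeals can act on the components of the primary endpoint: stool frequency, rectal bleeding and endoscopic appearance. Protocol 5.4.1 itself warns that changes in allowed UC medication may confound efficacy, and Table 5-2 is headed as agents that may affect efficacy assessment. That worry is carried into conduct rules but not into the endpoint definition.

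A subject who adds such therapy and still has a complete Week 10 assessment is therefore credited to the randomized arm. If added therapy is commoner on placebo, the placebo rate rises and the difference shrinks. If it is commoner on active drug, the reverse holds. The documents do not say which to expect.

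**Working it through.** **1. Which subjects escape the indirect protection?**

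| Situation | Week 10 endoscopic subscore | Scored as |
|---|---|---|
| Change found and subject withdrawn before the Week 10 endoscopy | None (Protocol Appendix 2 has no endoscopy at early termination) | Non-responder, by imputation |
| Change not found, or not acted on, before the Week 10 endoscopy | Present | Observed values |
| Study drug stopped, but endoscopy still done within the window | Present | Observed values |

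The second and third rows are the gap. Four features of the plan allow them:
- The visits in Protocol Appendix 2 are at Day 43 (Week 6) and Day 71 (Week 10), with none between: 71 − 43 = 28 days.
- Protocol 6.5.2 gives every subject who attends Week 10 an endoscopy.
- SAP Table 3-1 assigns to Week 10 any endoscopy from Day 58 to the earlier of Day 85 and open-label Day 1, whether or not the subject is still on treatment.
- SAP Appendix 4 averages 3 evaluable diary days from the 7 before the visit, so therapy added shortly before Week 10 can affect both diary subscores.

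**2. The plan's own power.** Inputs from SAP 1.3: 60 per arm, 22.5% versus 5%, Fisher's exact test, "1-sided 0.025 significance level". The stated result is that the design "will provide approximately 75% power when comparing each GS-4875 dose group to placebo".

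Power = Σₓ Σᵧ Bin(x; 60, p_A) · Bin(y; 60, p_P) · 1{P(X ≥ x | x + y) ≤ 0.025}, where the last probability is hypergeometric.

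With p_A = 0.225 and p_P = 0.05 this gives 75.1%, so the stated figure reproduces.

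**3. What one misclassified subject does under the planned design.** The assumed placebo rate is 5% × 60 = 3 remitters. One more adds 1/60 = 1.7 points. The counts below are assumptions.

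| Extra remitters (active, placebo) | Rates | Difference | Fisher power |
|---|---|---|---|
| 0, 0 | 22.5% vs 5.0% | 17.5 points | 75.1% |
| 0, 1 | 22.5% vs 6.7% | 15.8 points | 61.9% |
| 0, 2 | 22.5% vs 8.3% | 14.2 points | 48.6% |
| 0, 3 | 22.5% vs 10.0% | 12.5 points | 36.6% |
| 2, 2 | 25.8% vs 8.3% | 17.5 points | 65.6% |

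**4. How likely is one extra remitter?** Let c be the share of an arm that changes therapy and is still assessed. Let r be the share of those scored as remitters only because of the change. Then p_P = 0.05 + c_P·r and p_A = 0.225 + c_A·r. The documents give neither c nor r. Assume c_P of 5–10% and c_A of 2.5–5%.
- r = 5% at the lower change rates: p_P = 0.05 + 0.05 × 0.05 = 5.25% and p_A = 0.225 + 0.025 × 0.05 = 22.6%. Power is about 74%.
- r = 10% at the higher change rates: p_P = 0.05 + 0.10 × 0.10 = 6% and p_A = 0.225 + 0.05 × 0.10 = 23%. Power is about 70%.
- r = 25% at the lower change rates: 23.1% versus 6.25%. Power is 68.3%.
- r = 50% at the higher change rates: 25% versus 10%. Power is 49.4%.

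**5. What the current SAP will produce.** SAP 1.2 reports termination after 19 subjects enrolled. SAP 6.2.2 and 6.3.2 replace summaries and tests with by-subject listings of status. One misclassified subject is therefore one wrong yes/no entry per affected endpoint.

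**The case against.** The strongest defence is that the conduct rules already do the work: a subject withdrawn on time has no endoscopic subscore and fails by imputation. This stands for those subjects. A reader might infer that anyone who adds therapy between Weeks 6 and 10 is scored on observed values. The documents support that only where the change is not found or acted on before the endoscopy.

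A reader might also infer that such changes typically surface first at Week 10. That goes too far. The e-Diary is completed daily, a stool sample is to be taken whenever a subject becomes symptomatic (Protocol 6.9.5.4), and the medical monitor can be consulted before new UC medication is started (Protocol 5.4). Medication review is also scheduled at Week 10 itself. None of these guarantees earlier detection, so the supportable statement is that some changes may surface there.

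A fall in power to about 49% is likewise not established. It needs half of those who change therapy to reach remission, and even 25% exceeds the 22.5% the plan assumes for active drug. The power figures also belong to an analysis that has been dropped, and shifts in an arm's rate describe a summary the SAP will not produce.

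Finally, it would be wrong to say that the SAP lists no on-study medication. SAP 5.2 has the corticosteroid item, SAP 7.4.2 defines concomitant use to include starts after the first dose (though SAP 7.4 speaks of medication at baseline), and SAP 4.3 lists important deviations. What remains is narrower. The corticosteroid item carries no date or dose change, no comparable item covers the other UC agents, and the documents do not say that added therapy counts as an important deviation.

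**Conclusion.** The gap holds in a limited form. The written rule scores any subject with a complete Week 10 assessment on observed values, and the discontinuation rules close this only when they are applied before the endoscopy. A subject whose change is missed or not acted on by then can be listed as a remitter or responder, and the planned listings may not show it.

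The absence of the rule is certain from the text. Its frequency and direction are unknown, because the documents give no rate of therapy change. For the design as planned, the sensitivity is high because the assumed placebo rate is only 3 of 60: one extra placebo remitter takes Fisher power from 75.1% to 61.9%. For the study as terminated, the effect is confined to individual yes/no entries in the Week 10 listings.

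**What to change.** Add to SAP 6.1 and Protocol 8.5.1 a rule to this effect: a subject who, after the first dose of study drug and before the Week 10 assessments are complete, starts or increases above the Day 1 dose a UC medication named in Protocol 5.4.1, or takes a Table 5-2 agent, is a non-responder for all key efficacy endpoints regardless of observed scores. The starting point needs stating because every eligible subject has previously received a TNFα inhibitor, a class named in Table 5-2.

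Show the flag and the start date of the change in the response-status listing. SAP 1 provides for changes after finalization to be documented in the synoptic clinical study report, which is the natural place if the SAP is not reopened.

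Protocol 5.4.1 (study drug and study participation) and Protocol 5.4.2 and 6.13.3 (study drug only) differ on what is discontinued. They should be reconciled so that the analysis rule refers to one consistent procedure. Which reading is intended is for the sponsor to settle.

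The cost is one sentence and one derived flag from concomitant-medication data that Protocol 5.4 already requires on the eCRF. Patient management does not change. The small downside is that observed response rates may be slightly lower.

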6.1.1. Calculations of MCS and pMCS with the Subscores

The MCS is an instrument designed to measure disease activity in UC (Table 6-2). The MCS system is a composite index of 4 disease activity variables. Each variable is scored individually on an integer scale of 0 to 3, inclusive, with higher scores indicating greater disease activity. The

individual components of the MCS include Stool Frequency, Rectal Bleeding, Endoscopic Findings subscore, and the Physician’s Global Assessment (PGA). Stool Frequency and Rectal Bleeding are determined using an electronic daily diary, which collects subject reported components directly.

The efficacy endpoints described in [Table 6-1](#), except for Histologic Remission, are all based on the 4 individual components. MCS is calculated as the sum of the 4 subscores, ranging from 0 to 12. A pMCS is calculated as the sum of the 3 subscores excluding the Endoscopic subscore, ranging from 0 to 9. Further information on the MCS and calculation rules are listed in [Appendix 4](#).

Table 6-2. Modified Mayo Clinic Score (MCS)

Variables	Score			
	0	1	2	3
Stool Frequency	Normal number of stools for subject	1 to 2 stools per day more than normal	3 to 4 stools per day more than normal	≥ 5 stools per day more than normal
Rectal Bleeding	No blood seen	Streaks of blood with stool less than half the time	Obvious blood or streaks of blood with stool most of the time	Blood alone passes
Endoscopic Findings	Normal or inactive disease	Mild disease	Moderate disease	Severe disease
Physician Global Assessment	Normal	Mild disease	Moderate disease	Severe disease

A by-subject listing will be provided by subject ID number and visit for the following scores:

- MCS
- MCS subscores in Stool Frequency, Rectal Bleeding, Endoscopic Findings (locally and centrally read), and PGA
- pMCS

6.2. Primary Efficacy Endpoints

6.2.1. Definition of the Primary Efficacy Endpoints

The primary efficacy endpoint is the proportion of subjects achieving Clinical Remission per Modified MCS at Week 10, as defined in [Table 6-1](#). MCS subscores collected at Screening will be used as baseline values.

6.2.2. Analysis of the Primary Efficacy Endpoint

Due to limited subject enrollment in the study, the summary of primary efficacy endpoint will not be provided. No statistical testing will be performed. A by-subject listing of Clinical Remission status per Modified MCS at Week 10 will be provided by subject ID number.

